7.1 Study Schedule

	Pre-Study/ Screening (within 6 weeks of Day 1 of Study)	Day 1 Study Visit	End of Every Month (+/- 2 weeks)	End of Every 3 Months (+/- 2 weeks)	End of Month 12 Study Visit (+/- 2 weeks)	Follow Up Visit ¹ (6 months after completion of STAND clinic)
Physical Exam with Health Care Provider (Both study arms)	X	X		X	X	X
LHRH Analogue ^a		X		X		
Exercise, Nutrition, Symptom Management counseling ^b		X	X			
Educational Modules (STAND clinic arm only)		X	X			
Counseling, review tests and questionnaires				X	X	X
Informed Consent	X					
Randomization	X					
Demographics	X					
Past Medical History	X					
Concomitant Medications ⁱ	X	X		X	X	
QOL/empathy Questionnaires ^c		X		X	X	X
Co-morbidity Assessment ^d	X					
Ratio of 2 nd to 4 th digit finger length ^e	X					
Weight/Body Mass Index/Percent Body Fat ^f	X	X		X	X	X
ECOG Performance		X		X	X	

DXA Scan ^f	X				X	
HRpQCT (optional) ^h	X				X	
Serum PSA ⁱ	X	X		X	X	X
Serum testosterone		X ^j			X	X
Serum 25-(OH) vitamin D level		X		X	X	
Fasting glucose/lipid panel, HgbA1c, insulin level		X		X	X	X
Hemoglobin A1c		X		X	X	X
Plasma/serum for banking ^k		X		X	X	X
PBMCs for germline polymorphisms (optional) ^k		X				

a. Patients who have started ADT prior to study enrollment will be kept on same schedule for next dose of LHRH analog and provider visit while on study. On study patients will receive LHRH agonist every 3 months (+/- 1 week), on same day as health care provider visits whenever possible.

b. Patients randomized to the STAND clinic will visit with one of three specialties (exercise, nutrition, symptom management) at each monthly visit. The total number of visits with each specialty will be four on an every 3-month basis. The rotation of the schedule of providers may be adjusted depending upon availability of provider and patient. Patients randomized to the usual care study arm will be referred to nutrition, exercise, and symptom management services upon patient request or as deemed necessary by health care provider.

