c. Quality of life questionnaires to be completed include SF-12, EPIC-26, Hot Flash Related Daily Interference Scale, Lee Fatigue Scale, PHQ-9, Attentional Functional Index, Exercise questionnaires, and empathy quotient-8 (see Appendix 2). These questionnaires may be completed online ahead of scheduled visit or at the time of clinic visit, either electronically or on paper. The PHQ-9 scale must be completed on paper on the same day as study visit, and reviewed and signed by health care provider prior to patient discharge from clinic.

d. Assessed with Charlson Comorbidity Index (see Appendix 3)

e. Measured by caliper (see Section 1). For patients already enrolled on study who did not complete at baseline, this measurement will be performed at the next planned study visit.

f. Percent body fat to be measured using bioimpedance device on C1D1, every 3 months, and end of month 12 on study (see Appendix 4)

g. Bone mineral density measured at the lumbar spine, total hip, and femoral neck (performed within 12 weeks of day 1 of study)

h. High resolution quantitative peripheral CT of the radius and tibia (optional)

i. Baseline PSA determined during screening if not already taking ADT

j. Include screening assessment or serum testosterone of prior receipt of ADT

k. See Appendix 6 for collection and processing instructions

l. Following completion of STAND clinic participation, patients will be followed by telephone visit after 2 and 4 months to assess adherence to recommended diet/exercise plans. At 6 months, patients will return for clinic assessment.

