7.2 Screening Visit (within 6 weeks of Day 1 of Study)

Screening procedures and informed consent as well as written health information authorization must be completed within 6 weeks of day 1 of study. All research-related procedures will be conducted after patient has signed written consent to participate in the study.

These procedures include:

- Physical exam and medical history
- Demographics and disease characteristics:
 - Date of prostate cancer diagnosis
 - Gleason grade and PSA at the time of diagnosis
 - Type and date of prior local therapy (if any)
 - Date of ADT initiation and indication (adjuvant, biochemical relapse, or metastatic disease)
 - Concurrent use of anti-androgen (yes/no)
 - Concurrent radiation therapy (yes/no)
 - Metastatic status at time of study entry (none, bone only, soft tissue, any visceral)

Clinical Assessment

- Co-morbidity assessment by Charlson Co-morbidity Scale (Appendix 3)
- Quality of life questionnaires (see Appendix 2):
 - SF-12, EPIC-26, HFRDIS, Lee Fatigue Scale, PHQ-9, Attentional Functional Index, exercise patterns, empathy scale
- Concomitant medication
- Weight and body mass index
- Assessment of ratio of 2nd digit to 4th digit finger length using caliper assessment

Radiographic Assessment

- DXA Bone Density Scan (completed within 12 weeks of Day 1 of study)
- High resolution peripheral quantitative CT scan of the distal tibia and radius (optional)

Laboratory Assessment

- Baseline PSA measurement
- Serum testosterone (if prior receipt of androgen deprivation therapy)

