7.3 Randomization

Once eligibility is confirmed and patient has signed informed consent, patients will be stratified according to duration of ADT prior to study entry (≤ 3 months vs. 3-6 months) and body mass index at study entry (≤ 30 vs. > 30). They will be randomized with equal probability to one of the two study arms from within each of the six strata. Balance in treatment assignment will be achieved using a randomized block design. Randomization will be carried out via computer generated random assignment. Randomization must be completed within 6 weeks of day 1 of study.

A non-randomized pilot cohort of patients receiving concurrent chemohormonal therapy will be enrolled in parallel to assess the feasibility of STAND clinic participation in this patient population.

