7.4 Day 1 Study Visit

7.4.1 Clinical Assessment

- Physical examination
- Concomitant medications
- ECOG Performance Status
- Height, weight, body mass index, and percent body fat by bioimpedance measurement (see Appendix 6)
- LHRH Analogue

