7.5 Day 1 and Monthly Study Visits (+/- 2 weeks)

Patients randomized to the STAND clinic will return to clinic on a monthly basis. During the course of these monthly visits, there will be a series of self-guided educational modules discussing various aspects of androgen deprivation therapy and management of side effects.

These modules will be comprised of PowerPoint slide presentations which the patients will view on a self-directed manner during their clinic visit, with the opportunity to ask questions before and after the presentation. In addition, on a rotating schedule, patients will meet one-to-one with a licensed exercise trainer, registered dietitian, and symptom management service to receive individualized counseling. The rotation of the schedule of providers may be adjusted depending upon availability of provider and patient. In total, patients will meet with each specialized service four times on a rotating every 3 month-schedule.

Patients enrolled in the non-randomized chemohormonal cohort will return to clinic on an approximately monthly basis for rotating visits with exercise, nutrition, and symptom management, with schedule of visits matching whenever possible the scheduled dates of infusion center appointments

Patients randomized to the standard-of-care arm will be referred to nutrition, exercise, and symptom management service upon patient request or if deemed necessary by health care provider, as per current standard-of-care and practice guidelines. Patients will have the opportunity to receive the educational modules for review outside the clinic setting

During the course of the visit with the exercise trainer, patients will review exercise patterns with the use of questionnaires filled out prior to visit and via the use of ambulatory accelerometer which quantifies activity level. Patients will receive individualized counseling regarding specific exercises, and reinforcement of establishing regular exercise routine. During the course of the visit, patients will have the opportunity to practice actual exercise routines under the supervision of the exercise trainer, and will receive in-person assessment of aerobic fitness level.

During the course of the visit with the registered dietitian, patients will review dietary habits with the use of diet logs filled out prior to each visit. Patients will receive individualized counseling on recommended foods/diet, and will receive feedback on progress on a longitudinal basis.

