8.1 Percent Body Fat Estimation

Percent body fat will be estimated at baseline and every 3 months with the use of standard bioelectrical impedance monitor (see Appendix 4). Prior studies have demonstrated high reliability and strong correlation with other modalities including DXA scans.

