9.5 Analysis Populations

The primary analysis for the randomized cohort will include all patients who have a body fat % measurement at baseline and at month 12 on study (± 2 weeks). If a patient comes off study prior to obtaining the end of month 12 body fat % measurement, they will not be included in the primary study analysis.

All patients enrolled in the chemohormonal non-randomized cohort who complete C1D1 visit will be included in the analysis of the primary endpoint, the percentage of completed visits in the STAND clinic.

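### The baseline body-fat reading for the primary endpoint is due on Day 1, up to 6 weeks after unblinded allocation, and no analysis section names the baseline visit

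*Combined protocol and SAP*

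**What the plan says.** **When body fat is measured.** Footnote f in 7.1 reads: "Percent body fat to be measured using bioimpedance device on C1D1, every 3 months, and end of month 12 on study". Section 7.4.1 lists, for Day 1, "Height, weight, body mass index, and percent body fat by bioimpedance measurement". Section 7.2 lists only "Weight and body mass index" among the screening measurements. The schedule table has one combined row, "Weight/Body Mass Index/Percent Body Fat", and marks it at both screening and Day 1.

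**When men are randomised.** The schedule marks randomisation in the screening column. Section 7.3 adds: "Randomization must be completed within 6 weeks of day 1 of study". It sets a maximum gap but no minimum.

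**When STAND begins.** Educational modules and specialty counselling are first marked on Day 1. The order of the body-fat reading and the counselling on that day is not given.

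**What the analysis calls baseline.** Section 8.1 says "Percent body fat will be estimated at baseline and every 3 months". Section 9.5 includes "all patients who have a body fat % measurement at baseline and at month 12 on study". Sections 9.7.1 and 9.8.1 also refer to baseline. None of them names a visit.

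**Blinding.** None is described, and the arms differ visibly: monthly clinic attendance with rotating counselling against 3-monthly provider visits.

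**The concern.** The primary endpoint is the percent change in percentage body fat, so the baseline value enters twice, as the subtrahend and as the denominator. Randomisation makes the arms comparable up to the moment of allocation. Anything measured after a man knows his arm can differ between arms because of that knowledge.

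This is a diet and exercise trial. A man told that he will attend STAND may change his habits at once, and part of his response would then sit in his baseline and the effect would be understated. He may instead relax until the programme starts, which would raise his baseline and overstate the effect. Men told that they are in usual care may also react either way. No section requires a body-fat reading before allocation, so a shift of this kind could not be detected or corrected from the data.

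A smaller matter is that the table and the text do not match, and the analysis sections do not settle which visit supplies the baseline.

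**Working it through.** **1. The passages side by side**

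| Source | Screening | Day 1 |
|---|---|---|
| 7.1 table, combined row | marked | marked |
| 7.1 footnote f, percent body fat | not listed | listed |
| 7.2, percent body fat | not listed | not applicable |
| 7.4.1, percent body fat | not applicable | listed |
| 7.1 table, randomisation | marked | not marked |
| 7.1 table, STAND modules and counselling | not marked | marked |

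Three texts place the first required reading on Day 1, and the order is randomisation first, reading second. The gap is 0 to 6 weeks.

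**2. The plan's own sample size (9.2)**

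Inputs: usual-care mean change 12%, SD 17%, STAND mean change 0%, 32 evaluable per arm, two-sample t test, two-sided 0.05.

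- Effect size: 12/17 = 0.706, which the plan gives as 0.71.
- Power at 32 per arm (noncentral t): 79.8% at 0.71 and 79.4% at 12/17. The plan states 80%.
- Enrolment: 32/(1 − 0.20) = 40 per arm, as stated.

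The plan's figures reproduce.

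**3. How far a post-allocation baseline could move the result**

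Assumptions that are not in the documents: usual-care men gain linearly at 12 points per 52 weeks from allocation, on a scale where body fat at allocation is 100; every STAND man holds flat from allocation; the SD stays at 17. Month 12 is counted from Day 1, as the schedule's columns and the wording of 9.5 indicate, so Day 1 to month 12 is a full 52 weeks.

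With the maximum gap of 6 weeks:

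- Usual care at Day 1: 100 + 12 × 6/52 = 101.38.
- Usual-care percent change, Day 1 to month 12: 12/101.38 = 11.84%.
- STAND percent change: 0%.
- Difference: 11.84 points. Effect size: 11.84/17 = 0.696. Power at 32 per arm: 78.3%, against 79.4%.

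With a 3-week gap:

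- Usual care at Day 1: 100 + 12 × 3/52 = 100.69.
- Difference: 12/100.69 = 11.92 points. Effect size: 0.701. Power: 78.8%.

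With no gap, or no change in behaviour before Day 1, nothing is lost.

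Measured from allocation, the 6-week case would show 12 × 58/52 = 13.38 points over 58 weeks. The Day 1 baseline gives up that extra 1.38 and, through the slightly larger denominator, 0.16 of the planned 12.

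**The case against.** The strongest reply is that the text is consistent and the exposure slight. Footnote f, 7.2 and 7.4.1 all point to Day 1. Weight and BMI explain the screening mark in the combined row, and BMI is needed there for stratification. No STAND session takes place before Day 1, so only anticipation could move the reading, and 6 weeks is the longest gap allowed. Day 1 is also a natural start for the 12-month interval. Most of this stands, and it limits three stronger readings that a reader might infer:

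- **That the plan defines two competing baselines.** It does not. The table mark is ambiguous, but no text requires a screening body-fat reading. The ambiguity still deserves tidying. Footnote f is not a complete list, since it omits the 6-month follow-up reading that the table and 7.9 require.
- **That a 6-week gap removes 6/52 of the planned 12 points.** That would hold if month 12 were counted from randomisation, or if the total benefit were capped at 12 points. The documents say neither, and the follow-up clock starts on Day 1.
- **That men who leave between allocation and Day 1 are lost because of the Day 1 baseline.** Such a man has no month 12 reading either, so 9.5 and 9.8.1 exclude him whichever baseline is used. That is a separate complete-case matter.

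The reply does not remove the order of events. Allocation can come first, the arms are recognisable, and nothing requires the reading to precede disclosure, or even to precede counselling on Day 1. Section 7.5 also has diet logs and exercise questionnaires completed ahead of the specialty visits. A STAND man whose first session is nutrition or exercise may therefore be recording his habits before his baseline is read.

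**Conclusion.** The point holds in a limited form. The baseline of the primary endpoint can be read after a man knows his arm, and the analysis sections do not say which visit supplies it. The stated sample size and significance level are unaffected.

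The likely bias is small. Under the linear-gain, flat-from-allocation assumption at the maximum gap, it is 0.16 of 12 points and about 1 percentage point of power. That figure is an illustration: it rests on a constant rate of gain, an unchanged SD and follow-up counted from Day 1. A one-off change in habits before Day 1 would have a different effect, and the documents give no figure from which to size it. The direction is not fixed either, so the result should not be described as biased for or against STAND. The case for acting is that the exposure is avoidable at almost no cost.

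**What to change.** Require the baseline bioimpedance reading before the allocation is disclosed, by one of two routes.

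1. **Release the allocation only after the Day 1 reading**, by amending 7.3 and the randomisation row of 7.1. This keeps the 12-month interval and also settles the order of reading and counselling. The cost is that the first STAND session cannot be booked by arm before Day 1.
2. **Take the reading at screening, before randomisation**, by adding it to 7.2 and footnote f. BMI is already measured at that visit. The cost is a change interval up to 6 weeks longer in both arms, which for men not yet on ADT may include time before ADT. The Day 1 reading can be kept for a sensitivity analysis.

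Under either route, name the chosen reading as baseline in 9.5, 9.7.1 and 9.8.1, carry the same term into 8.1, and give percent body fat its own schedule row so that the table and footnote f agree. Beyond the costs named above, this is a change of wording, plus one short extra measurement under the second route.

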7.2 Screening Visit (within 6 weeks of Day 1 of Study)

Screening procedures and informed consent as well as written health information authorization must be completed within 6 weeks of day 1 of study. All research-related procedures will be conducted after patient has signed written consent to participate in the study.

These procedures include:

- Physical exam and medical history
- Demographics and disease characteristics:
 - Date of prostate cancer diagnosis
 - Gleason grade and PSA at the time of diagnosis
 - Type and date of prior local therapy (if any)
 - Date of ADT initiation and indication (adjuvant, biochemical relapse, or metastatic disease)
 - Concurrent use of anti-androgen (yes/no)
 - Concurrent radiation therapy (yes/no)
 - Metastatic status at time of study entry (none, bone only, soft tissue, any visceral)

Clinical Assessment

- Co-morbidity assessment by Charlson Co-morbidity Scale (Appendix 3)
- Quality of life questionnaires (see Appendix 2):
 - SF-12, EPIC-26, HFRDIS, Lee Fatigue Scale, PHQ-9, Attentional Functional Index, exercise patterns, empathy scale
- Concomitant medication
- Weight and body mass index
- Assessment of ratio of 2nd digit to 4th digit finger length using caliper assessment

Radiographic Assessment

- DXA Bone Density Scan (completed within 12 weeks of Day 1 of study)
- High resolution peripheral quantitative CT scan of the distal tibia and radius (optional)

Laboratory Assessment

- Baseline PSA measurement
- Serum testosterone (if prior receipt of androgen deprivation therapy)

7.3 Randomization

Once eligibility is confirmed and patient has signed informed consent, patients will be stratified according to duration of ADT prior to study entry (≤ 3 months vs. 3-6 months) and body mass index at study entry (≤ 30 vs. > 30). They will be randomized with equal probability to one of the two study arms from within each of the six strata. Balance in treatment assignment will be achieved using a randomized block design. Randomization will be carried out via computer generated random assignment. Randomization must be completed within 6 weeks of day 1 of study.

A non-randomized pilot cohort of patients receiving concurrent chemohormonal therapy will be enrolled in parallel to assess the feasibility of STAND clinic participation in this patient population.

7.4 Day 1 Study Visit

7.4.1 Clinical Assessment

- Physical examination
- Concomitant medications
- ECOG Performance Status
- Height, weight, body mass index, and percent body fat by bioimpedance measurement (see Appendix 6)
- LHRH Analogue

7.4.2 Laboratory Assessment

- Optional Peripheral blood collection for genotyping
- Extra serum and PBMCs collection for banking
- Fasting lipid panel (total cholesterol, triglycerides, LDL, HDL), glucose, insulin levels
- Hemoglobin A1c
- Serum 25-(OH) vitamin D level
- Serum PSA
- Serum testosterone

7.5 Day 1 and Monthly Study Visits (+/- 2 weeks)

Patients randomized to the STAND clinic will return to clinic on a monthly basis. During the course of these monthly visits, there will be a series of self-guided educational modules discussing various aspects of androgen deprivation therapy and management of side effects.

These modules will be comprised of PowerPoint slide presentations which the patients will view on a self-directed manner during their clinic visit, with the opportunity to ask questions before and after the presentation. In addition, on a rotating schedule, patients will meet one-to-one with a licensed exercise trainer, registered dietitian, and symptom management service to receive individualized counseling. The rotation of the schedule of providers may be adjusted depending upon availability of provider and patient. In total, patients will meet with each specialized service four times on a rotating every 3 month-schedule.

Patients enrolled in the non-randomized chemohormonal cohort will return to clinic on an approximately monthly basis for rotating visits with exercise, nutrition, and symptom management, with schedule of visits matching whenever possible the scheduled dates of infusion center appointments

Patients randomized to the standard-of-care arm will be referred to nutrition, exercise, and symptom management service upon patient request or if deemed necessary by health care provider, as per current standard-of-care and practice guidelines. Patients will have the opportunity to receive the educational modules for review outside the clinic setting

During the course of the visit with the exercise trainer, patients will review exercise patterns with the use of questionnaires filled out prior to visit and via the use of ambulatory accelerometer which quantifies activity level. Patients will receive individualized counseling regarding specific exercises, and reinforcement of establishing regular exercise routine. During the course of the visit, patients will have the opportunity to practice actual exercise routines under the supervision of the exercise trainer, and will receive in-person assessment of aerobic fitness level.

During the course of the visit with the registered dietitian, patients will review dietary habits with the use of diet logs filled out prior to each visit. Patients will receive individualized counseling on recommended foods/diet, and will receive feedback on progress on a longitudinal basis.

During the course of visit with symptom management service, patients physical and psychosocial issues will be addressed by trained health care provider. Counseling and medical management will be provided.

7.6 Every 3 Month Study Visits (+/- 2 weeks)

7.6.1 Clinical Assessment

- Physical exam
- Concomitant medications
- ECOG Performance Status
- Quality of life questionnaires
 - SF-12, EPIC-26, HFRDIS, Lee Fatigue Scale, PHQ-9, Attentional Functional Index, exercise pattern assessment, empathy scale

- Weight, body mass index, and percent body fat by bioimpedance measurement
- Patients will be referred to the Symptom Management Service, nutrition service, and/or exercise physiologist for further evaluation at the discretion of health care provider or per patient request (Standard-of-care treatment arm only)
- LHRH analogue administration
- Counseling regarding lifestyle modifications and review of the results of the above laboratory tests and quality of life questionnaires by a trained nurse practitioner or physician.
 - The PHQ-9 questionnaire screening for depression must be completed in person during the study visit and must be signed by treating health care provider prior to patient discharge from clinic

